### **Cumulative Dose**

The overall cumulative dose (mg/kg) of avelumab per subject across all cycles is the sum of the actual dose levels that the subject received (i.e. total dose administered (mg) / weight (kg)).

The overall cumulative dose (mg/m^2) of oxaliplatin, 5-FU, and capecitabine per subject across all cycles is the sum of the actual dose levels that the subject received (i.e. total dose administered (mg) / BSA (m^2)).

### **Dose Intensity**

The dose intensity (DI) will be calculated for each subject across all cycles. Each cycle is defined by a 2-week period for avelumab and oxaliplatin + 5-FU and by a 3-week period for Oxaliplatin + Capecitabine.

The dose intensity of avelumab (mg/kg/cycle), oxaliplatin (mg/m^2/cycle), 5-FU (mg/m^2/cycle), and capecitabine (mg/m^2/cycle) is defined as

$$DI = \left( \frac{\text{cumulative dose}}{\frac{\text{duration of therapy (in weeks)}}{\text{number of weeks per cycle}}} \right)$$

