The extent of exposure to randomized treatment (ie, avelumab or maintenance chemotherapy) will be characterized by duration (weeks), number of administrations, cumulative dose (eg, mg/kg or mg/m²), dose intensity (mg/kg/week or mg/m²/week), relative dose intensity (actual dose given / planned dose), number of dose delays, and number of infusion rate reductions (avelumab arm only), for the Safety-Maintenance Analysis Set. The number and percentage of non-compliant subjects (see Section 6.9) with regard to randomized treatment will be presented by treatment arm based on the Safety-Maintenance Analysis Set.

Prior Anti-Cancer Therapies and Procedures

Prior anti-cancer therapies (ie, anti-cancer medications other than trial treatment taken at any time prior to ICF signature) will be summarized using frequencies and percentages by drug class and preferred name within treatment arm and overall for the Safety-Induction Analysis Set and Safety-Maintenance Analysis Set. A similar summary will be provided by drug class, preferred name, and total subjects for the Safety-Induction Analysis Set. Prior anti-cancer procedures (ie, procedures undertaken at any time prior to ICF signature) will be listed only.

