## 8 Changes to the Planned Analyses in the Clinical Trial Protocol

The statistical methods specified in this SAP are in accordance with protocol version 7.0 (dated 17 July 2019), with the following exception:

- Subjects randomized to the chemotherapy arm, who are designated to receive BSC-only, will have the date of their Week 1 Day 1 assessment considered as “treatment start date”. Consequently, this date will be used for determining baseline for Safety endpoints. This differs from the protocol, which specifies that the date of randomization will be used for both. Use of the Week 1 Day 1 assessment date more closely mirrors how subjects randomized to active treatment are handled.

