### **Relative Dose Intensity**

The relative dose intensity (RDI) is defined as the actual dose intensity divided by the planned dose per cycle and expressed in %.

The summary of treatment exposure and compliance will be calculated for both Induction Phase and Maintenance Phase, and will include the following information:

- Duration of therapy (weeks)
- Total number of infusions received (avelumab and IV chemotherapy)
- Total number of Capecitabine doses received

The following will be included, broken down by separate chemotherapy treatment in the chemotherapy arm:

- Cumulative dose of therapy (mg/kg or mg/m^2)
  - Dose intensity (mg/kg/cycle) or (mg/m^2/cycle)
-

- Relative dose intensity of therapy categories: < 80%, 80% - < 90%, 90% - < 110%, >= 110%

A listing of treatment exposure and compliance will also be created to summarize the information listed above for each subject.

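### The SAP reports dose intensity per cycle where the protocol specifies per week, without declaring it, so any oxaliplatin mean taken across the two regimens reflects regimen mix

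*SAP*

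**What the plan says.** Protocol 8.5.6, under treatment exposure and compliance, lists for randomized treatment "dose intensity (mg/kg/week or mg/m²/week), relative dose intensity (actual dose given / planned dose". It gives no unit for Induction Phase exposure, which it summarizes for all subjects together.

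SAP 14 uses a per-cycle unit: "The dose intensity of avelumab (mg/kg/cycle", and mg/m² per cycle for oxaliplatin, 5-FU and capecitabine. The divisor is duration in weeks over weeks per cycle. On cycle length it says "Each cycle is defined by a 2-week period for avelumab and oxaliplatin + 5-FU", with 3 weeks for oxaliplatin + capecitabine. Relative dose intensity (RDI) "is defined as the actual dose intensity divided by the planned dose per cycle".

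SAP 14 applies the exposure summary to both phases and splits it within the chemotherapy arm by separate treatment, without saying whether that means by drug or by regimen. SAP 10 sets the columns: the two chemotherapy regimens plus an overall column for Induction, and avelumab against one combined chemotherapy/BSC column for Maintenance.

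SAP 8 states that its methods are "in accordance with protocol version 7.0 (dated 17 July 2019), with the following exception". The single exception concerns the treatment start date for subjects on best supportive care only.

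**The concern.** A weekly unit puts schedules of different length on one time scale. The control arm and the Induction Phase both contain such schedules: oxaliplatin every 2 weeks with 5-FU and every 3 weeks with capecitabine. Under the per-cycle unit the two regimens are measured in different units that share a label. A mean over both then says more about how many subjects received each regimen than about how much oxaliplatin they received per unit of time. A reader who relies on SAP 8 would also believe that the exposure tables follow the protocol's unit, which they do not.

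**Working it through.** **Inputs.** Planned oxaliplatin is 85 mg/m² every 2 weeks with 5-FU and 130 mg/m² every 3 weeks with capecitabine (Protocol 6.2.2). Duration in weeks is (last dose date − first dose date + 14)/7 for avelumab and for oxaliplatin with 5-FU, and the same with +21 for oxaliplatin with capecitabine (SAP 14). Neither document states an expected dose intensity, so there is no figure to reproduce.

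**Are the SAP formulas coherent?** Take full doses on schedule for 12 weeks.

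- Oxaliplatin with 5-FU: 6 × 85 = 510 mg/m² over 12/2 = 6 cycles gives 85 per cycle; RDI 85/85 = 100%.
- Oxaliplatin with capecitabine: 4 × 130 = 520 mg/m² over 12/3 = 4 cycles gives 130 per cycle; RDI 130/130 = 100%.

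The formulas return the planned doses. The issue is the unit.

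**Effect of the unit.**

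| Full-dose oxaliplatin | with 5-FU | with capecitabine | ratio |
|---|---|---|---|
| mg/m² per cycle (SAP) | 85 | 130 | 130/85 = 1.53 |
| mg/m² per week (protocol unit) | 85/2 = 42.5 | 130/3 = 43.3 | 43.3/42.5 = 1.02 |

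**Effect on a pooled mean.** Let p be the share of subjects on capecitabine. The documents do not give p, so it is varied. Per cycle the full-dose mean is 85(1 − p) + 130p; per week it is 42.5(1 − p) + 43.3p.

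| p (assumed) | per cycle | per week |
|---|---|---|
| 30% | 98.5 | 42.8 |
| 50% | 107.5 | 42.9 |
| 70% | 116.5 | 43.1 |

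Every subject here receives full doses on time, so all movement in the per-cycle column is regimen mix.

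**Where pooling arises.** The overall Induction column is the default under SAP 10. The combined Maintenance column pools oxaliplatin if the split in SAP 14 is by drug. Avelumab, 5-FU and capecitabine each have one cycle length, so only oxaliplatin mixes units.

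**RDI.** Write C for cumulative dose, D for duration in weeks, w for weeks per cycle and P for planned dose per cycle. The SAP's RDI is [C/(D/w)]/P = Cw/(DP). A weekly version is (C/D)/(P/w) = Cw/(DP). They are identical, so changing the unit of dose intensity leaves every RDI value and category as it is.

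The protocol's RDI has no stated period for the planned dose. Take six full avelumab doses with one 2-week gap (Days 1, 15, 29, 57, 71, 85). D = (84 + 14)/7 = 14 weeks, or 7 cycles, and the SAP gives 60/7/10 = 85.7%. If the protocol means the dose planned over elapsed time, it gives 60/(7 × 10) = 85.7%, the same. If it means the dose planned for the administrations received, it gives 60/60 = 100%. A 25% oxaliplatin reduction given on schedule is 75% on every reading.

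**The case against.** Protocol 8.5.1 allows the SAP to modify the protocol's plans and requires an amendment only for major modifications; a unit in a descriptive table is not major. The SAP labels the unit, and a reader can divide by 2 or 3. RDI is unitless and gives 100% for full dose on either regimen, so a measure comparable across regimens already exists. No comparison of oxaliplatin between regimens is planned, and Induction results are also shown by regimen. All of this stands and limits the point to a small one. It does not rescue the pooled figure: once subjects on 2-week and 3-week cycles are averaged, a reader cannot convert the mean without knowing the mix. Nor does the freedom to modify explain why SAP 8 claims accord with the protocol apart from one unrelated exception.

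Two stronger readings are tempting, and the documents do not support them.

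- **That the same subject necessarily gets a different RDI under the two documents.** The protocol says only "relative dose intensity (actual dose given / planned dose", with no period. The definitions differ for delayed or omitted doses on one reading and agree on the other. Repeated 16-day avelumab intervals might seem to show a subject with no recorded delay falling to 89%: dose 6 is on Day 81, D = (80 + 14)/7 = 13.43 weeks, and 60/6.71/10 = 89.4%. But Protocol 7.1.4 tells subjects to return to the target date, with a window of −4/+2 days. Dose 6 is due on Day 71 and no later than Day 73, which gives 60/[((72 + 14)/7)/2]/10 = 97.7%.
- **That a low RDI cannot be traced to reduced or delayed doses.** SAP 14 separately summarizes chemotherapy dose reductions, delays to IV drugs by length, and IV interruptions with reasons, and adds listings by subject. Avelumab has no dose reductions.

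**Conclusion.** The mismatch in the unit of dose intensity is real and undeclared for randomized treatment, where the protocol fixes the unit. Its practical consequence is confined to oxaliplatin summarized across regimens: the overall Induction column by default, and the combined Maintenance column if the exposure split is by drug. There, two full-dose regimens 2% apart per week appear 53% apart, and the pooled full-dose mean shifts by 18 mg/m² per cycle (116.5 − 98.5) over the assumed 30% to 70% range of capecitabine use. The weekly intensities are close, not equal. The SAP's RDI is coherent and should stay; what is missing is a stated period for the protocol's planned dose. The point is minor. It touches descriptive exposure tables only and has no bearing on OS, PFS, BOR, alpha or power.

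**What to change.** In SAP 14, report dose intensity in mg/kg/week and mg/m²/week, computed as cumulative dose divided by duration in weeks, in line with Protocol 8.5.6. Alternatively, keep the per-cycle unit but present it by regimen only, in both phases, with no pooled oxaliplatin figure. List any difference that is retained in SAP 8. Leave the RDI formula as it is, and add one sentence saying that its denominator is the dose planned over elapsed treatment time, so that the protocol's wording is read the same way. The cost is a change of unit or of table layout and one or two sentences of text; no new data are needed.

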### **Relative Dose Intensity**

The relative dose intensity (RDI) is defined as the actual dose intensity divided by the planned dose per cycle and expressed in %.

The summary of treatment exposure and compliance will be calculated for both Induction Phase and Maintenance Phase, and will include the following information:

- Duration of therapy (weeks)
- Total number of infusions received (avelumab and IV chemotherapy)
- Total number of Capecitabine doses received

The following will be included, broken down by separate chemotherapy treatment in the chemotherapy arm:

- Cumulative dose of therapy (mg/kg or mg/m^2)
  - Dose intensity (mg/kg/cycle) or (mg/m^2/cycle)
-

- Relative dose intensity of therapy categories: < 80%, 80% - < 90%, 90% - < 110%, >= 110%

A listing of treatment exposure and compliance will also be created to summarize the information listed above for each subject.

### Dose Reductions

Dose reduction will be calculated for the chemotherapy arm only in the Maintenance Phase. Per study protocol, there will be no dose reductions for the avelumab treatment arm. A dose reduction is defined as an actual non-zero cumulative dose < 90% of the planned cumulative dose for a given treatment cycle. For subjects receiving Capecitabine or 5-FU as a push followed by a drip, any skipped doses within the cycle will be counted as part of the planned cumulative dose for the cycle (i.e. will contribute to the denominator of the calculation). Dose reductions are counted on a per-cycle basis and do not consider whether previous doses were reduced. The number of subjects with at least one dose reduction as well as a categorical breakdown of dose reductions (1 / 2 / 3 / >=4) will be summarized for the chemotherapy/BSC arm.

### Dose Delays

Dose delays will be calculated for Maintenance Phase IV study drugs only. Delays are defined as infusions given  $\geq 3$  days from the planned administration date and will be derived based on study drug administration date and will be grouped into the following categories based on the deviation of the actual to the planned treatment administration day (relative to the previous treatment administration date):

- No delay (including 1-2 days delays)
- 3-6 days delay
- 7 or more days delay

For example, if a subject receives avelumab on Day 1, then the next avelumab administration date should be on Day 15; however, if the subject receives avelumab on Day 16 or 17, this is considered as a “No delay”.

Number and percentage of subjects with delayed study drug administration and maximum length of delay, i.e. the worst case of delay if subjects have multiple dose delays will be summarized by treatment group.

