Additionally, subjects receiving avelumab who have experienced a CR should be treated for a minimum of 12 months or until disease progression or unacceptable toxicity, after confirmation of response. In case a subject with a confirmed CR relapses after stopping treatment, but prior to the end of the trial, 1 re-initiation of treatment is allowed at the discretion of the Investigator and after agreement with the Medical Monitor. In order to be eligible for retreatment, the subject must not have experienced any toxicity that led to treatment discontinuation of the initial avelumab therapy. Subjects who re-initiate treatment will stay on trial and will be treated and monitored according to the protocol and follow the Schedule of Assessments until disease progression (see [Table 3](#)).

The treatment should start within 4 days after randomization. While on trial treatment, subjects will be asked to visit the trial site as specified in the Schedule of Assessments (see [Table 3](#), [Table 4](#), [Table 5](#), and [Table 6](#)).

For both avelumab and maintenance chemotherapy, a time window of up to 4 days before or 2 day after the scheduled visit day (-4/ +2 days) will be permitted for all trial procedures. Subjects should return to the target date even if the previous visit was off schedule.

The tumor evaluation (see [Section 7.3](#)) will be performed every 6 weeks (for the first 12 months and every 12 weeks thereafter) with a time window of -5 days for both avelumab and maintenance chemotherapy.

Subjects will receive either:

- Avelumab by IV infusion following pretreatment (see [Section 5.1.2.2.1](#)) once every 2 weeks (see [Section 6.2.1](#)), or
- Maintenance chemotherapy following pretreatment as applicable prior to each infusion (see [Section 6.2.2](#)).

Assessments to be performed during the Maintenance Phase are presented in [Table 3](#) to [Table 6](#).

During the treatment period, the following assessments and procedures will be performed (see [Table 3](#) to [Table 6](#) for the detailed schedule):

- The subject-reported outcomes/QoL assessments will be completed by subjects prior to any trial-related procedures (time points outlined in [Table 3](#) to [Table 6](#)) and then every 6 weeks thereafter.
- AEs and concomitant medications and procedures will be documented at each visit.
- ECOG PS will be assessed at each treatment visit.

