### Dose Interruptions

An interruption is defined as an IV medication which is not administered (i.e. 0 dose) on one or more planned dosing days. Interruptions are identified on the [Study Drug] Administration eCRF pages (e.g. “Has the subject received a dose of Oxaliplatin during this visit?”). Please note that dose interruptions, as defined here, are not the same as drug interruptions captured on the Treatment Administration Modification Details eCRF page. The number and percentage of patients with dose

---

interruptions, the corresponding reasons, the number of interruptions observed, and the length of interruption will be summarized. Length of dose interruptions is measured in cycles.

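### The SAP counts dose delays from the previous infusion and not from the protocol's target date, so some in-window infusions, and infusions that follow a skipped dose, are reported as delays

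*SAP*

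**What the plan says.** SAP Section 14, Dose Delays, covers Maintenance Phase IV drugs. Delays "will be derived based on study drug administration date", and they are grouped by "the deviation of the actual to the planned treatment administration day (relative to the previous treatment administration date". The lowest category is "No delay (including 1-2 days delays", the next is 3 to 6 days, and the top one is "7 or more days delay". The worked example is: "if a subject receives avelumab on Day 1, then the next avelumab administration date should be on Day 15". The table reports the number of subjects with a delay and, for each subject, "the worst case of delay if subjects have multiple dose delays will be summarized by treatment group".

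Protocol Section 7.1.4 sets a window of -4/+2 days around the scheduled day for both arms and adds: "Subjects should return to the target date even if the previous visit was off schedule". SAP Appendix I lists a visit as a deviation only when it falls outside that window, with an exception for safety reasons.

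SAP Section 14, Dose Interruptions, has a separate count: "An interruption is defined as an IV medication which is not administered (i.e. 0 dose) on one or more planned dosing days". Its length is measured in cycles. Neither subsection says whether a gap that contains an interruption is left out of the delay count.

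SAP Section 8 states accordance with protocol version 7.0 apart from one exception, the treatment start date for subjects on best supportive care only. The delay reference point is not mentioned there.

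**The concern.** The two documents use different reference points. The protocol ties each infusion to a fixed target date, whereas the SAP ties it to the infusion before. A subject who comes early within the window and then returns to target, as the protocol asks, has a longer interval and can be recorded as delayed. The same infusion is then compliant in the deviation listing and delayed in the exposure table.

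An omitted dose lengthens the interval by a whole cycle, so the top delay category mixes omitted doses with late ones. Protocol Section 5.1.3.2 provides for such omissions of avelumab after an unresolved Grade 2 reaction.

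At stake is the readability of a by-arm table that describes how each regimen was delivered. Because subjects are classed by their worst delay, one artefact is enough to move a subject to another category.

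**Working it through.** **Inputs.** The cycle length C is 14 days for avelumab and oxaliplatin + 5-FU, and 21 days for oxaliplatin + capecitabine (SAP Section 14, Dose Intensity). The window is -4 to +2 days (Protocol Section 7.1.4). A delay is a deviation of 3 days or more (SAP Section 14).

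**Formula.** Let a and b be the offsets of two consecutive infusions from their target dates, with k doses skipped between them.
- SAP deviation = actual date − (previous actual date + C) = b − a + kC.
- Deviation from target = b.

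**The SAP's own example.** Day 1 plus 14 gives Day 15. Days 16 and 17 deviate by 1 and 2 days (no delay), and Day 18 would deviate by 3 (delay). This reproduces. The example starts on target, so both reference points give the same answer and it does not settle which is meant.

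**In-window pairs (k = 0).** There are 7 × 7 = 49 pairs. The condition b − a ≥ 3 holds for:
- a = -4: b = -1, 0, 1, 2 (4 pairs)
- a = -3: b = 0, 1, 2 (3 pairs)
- a = -2: b = 1, 2 (2 pairs)
- a = -1: b = 2 (1 pair)

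That is 10 of 49, with a maximum deviation of 2 − (-4) = 6 days, so in-window scheduling alone never reaches the top category. An exactly on-target infusion (b = 0) is flagged only when a is -3 or -4. Example: avelumab on Days 1, 11 and 29. The SAP plans the third infusion for Day 11 + 14 = Day 25 and records 29 − 25 = 4 days, although Day 29 is the target. Measured from target, none of the 49 pairs is a delay.

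**Skipped doses (a = b = 0).**
- One skip, then an infusion: deviation 14 days (2-week cycle) or 21 days (3-week cycle), plus one interruption.
- Two consecutive skips, 2-week cycle: one delay of 28 days.
- A skip with no later infusion: an interruption and no delay.

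**The opposite error.** With offsets 0, +2, +4, +6, +8, every SAP deviation is 2 days and nothing is flagged. Measured from target, the last three infusions are 4, 6 and 8 days late.

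**Share of subjects flagged.** Assume 8 infusions, the first on target, the others independent, and all inside the window. The second infusion cannot be flagged because it would need b ≥ 3. That leaves 6 pairs per subject. The expected number of false flags is 6 × (probability of a flagged pair), and the subject-level share was computed exactly from the same assumptions.

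| Assumed offsets | Probability of a flagged pair | Expected flags per subject | Subjects with at least one |
|---|---|---|---|
| 95% on target, rest evenly within 2 days | 3 × 0.0125² = 0.0005 | 0.003 | 0.3% |
| 80% on target, rest evenly within 2 days | 3 × 0.05² = 0.0075 | 0.045 | 4.4% |
| 80% on target, rest evenly over the window | 2 × 0.0333 × 0.8 + 8 × 0.0333² = 0.062 | 0.37 | 34% |
| Evenly over the whole window | 10/49 = 0.204 | 1.22 | 83% |

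In every row the true number of out-of-window infusions is zero.

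**The case against.** The SAP rule is explicit, and the protocol defines no competing one: Protocol Section 8.5.6 asks only for the number of dose delays. The interval since the last dose is a legitimate exposure measure, and window adherence is already reported as a protocol deviation. This stands as an argument for keeping the interval. It does not explain why an infusion that followed the protocol's return-to-target instruction should be labelled late, and Section 8 does not declare the difference.

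Counting from the target date alone would have its own fault. After one 7-day delay followed by regular 14-day dosing, every later infusion would be 7 days late, whereas the interval rule records one delay. Protocol Section 5.1.3.3 allows delays of chemotherapy for toxicity, and neither document defines a re-based schedule. This objection stands and shapes the fix.

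The rule is the same in both arms, no differential bias has been shown, and delays are listed with their reasons. That also stands.

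A reader might infer that on-schedule infusions are counted as delays in general, or that every skipped dose is counted twice. The documents support neither. An on-target infusion is flagged only after one given 3 or 4 days early. A final skip produces no delay, and a run of skips produces one. The overlap is between two separate summaries in different units, which the SAP does not add together.

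**Conclusion.** The point holds as a minor one. Taken with the protocol's scheduling rule, the SAP definition can class in-window infusions as delays of 3 to 6 days. It also places the first infusion after a skipped dose, or run of skips, in the top category in addition to the interruption count.

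The pair count and the skip results follow directly from the two documents, but 10 of 49 counts possible pairs and is not an expected rate. The range of 0.3% to 83% of subjects rests on assumed offsets, 8 infusions and independent visits. It depends mainly on how often infusions are given 3 or 4 days early, so no single value should be cited as the likely size.

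Only the descriptive exposure table is affected. Overall survival, the alpha allocation and power are not.

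**What to change.** In SAP Section 14, Dose Delays:
- Keep the interval from the previous infusion, so that one delay does not carry forward to later infusions.
- Do not count an infusion as a delay if it falls within -4/+2 days of its protocol target date.
- Do not count as a delay any gap that contains a 0-dose visit already reported as an interruption.

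The cost is a wording change and one further input to the exposure derivation, the scheduled visit date. Administration dates and 0-dose records are already collected. Two limits remain. A gradual drift of up to 2 days per cycle stays unflagged, as it does now. A late resumption after a skip would appear only through the interruption summary.
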